5.0 DELIVERY OF STEREOTACTIC BODY RADIATION THERAPY

5.1 Dose Specifications

5.1.1 The primary tumor(s) and any tumor vascular thrombus must be treated. Treatment volume will include both the residual TACE site, ethiodol marker, and any residual enhancing disease. Volume design is at the discretion of the radiation oncologist.

5.1.2 Treatment Schedule: All patients will receive radiation treatment with SBRT. Treatment will optimally be delivered every other day with no more than 3 fractions per week. The ideal treatment team will be less than 15 total days.

5.1.3 Prescription Dose: Radiation is to be delivered to 30-45 Gy in 5 fractions. 40 Gy in 5 fractions will be utilized, unless dose constraints preclude it.

5.1.4 Dose Specifications: The prescription isodose is planned to encompass 95% of PTV. The highest allowable doses to the target volumes that maintain normal tissue constraints should be used. A goal is that 100% of CTV is encompassed by the prescription dose.

5.1.5 Dose Prescription: Will be based on the volume of normal tissues irradiated based on mean liver dose and proximity to adjacent critical structures. In the absence of adjacent GI luminal structures that may limit dose (mean liver dose (MLD), as defined as liver minus GTV), prescription dose should be 40 Gy in 5 fractions. Vascular tumor thrombosis dose should be the same as the as the HCC prescription dose. However, lower doses are acceptable if require to meet normal tissue constraints. Non-tumor bland thrombosis is not recommended to be irradiated but can be included in the CTV if felt to be at risk for microscopic disease. Maximum dose within the PTV is 115% but below 110% is preferred. Maximum dose for any given axial slice should be

be within the PTV. Efforts should be made to keep the prescription dose as conformal as possible.

5.2 Technical Factors

5.2.1 Megavoltage equipment with photons of at least 6 MV, capable of daily cone beam CT imaging, with a multileaf collimator for intensity modulation is required. All plans should use IMRT.

5.2.2 CT based planning is required. A minimum of 5 beam angles is strongly recommended. Arc therapy is permitted.

5.2.3 Image guided radiation therapy (IGRT) is mandatory

5.2.4 Breathing motion is strongly management is strongly recommended if breathing motion is greater than 5 mm. Breathing motion assessed on 4D CT and adequately treated with PTV margins < 1 cm is encouraged.

5.3 Localization, Simulation, and Immobilization

5.3.1 Custom immobilization with an alphacradle or Vac-lock is required

5.3.2 Treatment planning CT scans will be required to define GTV. IV contrast is recommended for the planning CT. Oral contrast with simulation is encouraged.

5.3.3 Breathing motion is to be assessed using a 4D CT whenever possible. Use of an abdominal compression belt is encouraged as well, even when using a 4D CT. If 4D CT is not available, a breath hold technique is required.

5.3.4 Fusion or reference to a MRI with contrast is strongly encouraged to facilitate in defining treatment volumes.

5.4 Treatment Planning Volumes/ Target Volumes

5.4.1 The Gross Tumor Volume (GTV) is defined as all parenchymal and vascular HCC visualized on contrast enhanced CT and/or MRI, most often best seen on arterial phase or as wash out in venous or delayed phase. Non-tumor thrombi should not be considered part of the GTV. Liver-to-liver fusion with diagnostic MRI is recommended to facilitate treatment planning.

5.4.2 An Internal Target Volume (ITV) will be created when 4D CT simulation is used. This will be accomplished by contouring GTV through the binned respiratory cycle through each axial slice. If tumor is not visible, it is permitted to use 'surrogates' such as liver shape, defects, clips, etc. to estimate GTV location.

5.4.3 A Clinical Target Volume (CTV) is created by expanding the ITV to include additional areas of possible microscopic spread. Typical expansions are 5 to 10 mm beyond the ITV. CTV can be shaved off of natural barriers to spread (ie. chest wall, heart, etc.).

5.4.4 A Planning Target Volume (PTV) will be added to the CTV to compensate for set-up error and unaccounted organ motion (different breathing patterns on different days). The PTV expansion should be at that discretion of treating physician but will range from 5 to 10 mm.

5.4.5 All dose distributions shall include corrections for tissue heterogeneities. Arterial vascular contrast is recommended to be converted to water equivalent density if used for planning.

5.4.6 Goals of planning are to maximize dose to the target volumes, while maintaining all normal tissue constraints. Reducing the maximal dose to all luminal GI normal tissues should be a priority to reduce the risk of GI toxicity. Beam angles may be individualized to minimize the path length through the liver and through adjacent organs at risk. Conformality of the prescription dose is a secondary goal.

5.5 Critical Structures Maximal Doses

5.5.1 All dose values are provided as maximum total dose to be delivered in 5 equal fractions as follows:

Liver minus GTV	700cc receiving < 15 Gy
Esophagus max (to. 0.5 cc)	32 Gy
Stomach max (to 0.5 cc)	30 Gy
Duodenum max (to 0.5cc)	30 Gy
Small bowel max (to 0.5 cc)	30 Gy
Large bowel max (to 0.5 cc)	32 Gy
Cord + 5mm max (0.5cc)	25 Gy
Kidneys: bilateral mean dose	<10 Gy

OR – if one kidney mean dose > 10 Gy, remaining kidney V10 Gy < 10%

5.5.2 The following organ dose constraints are guidelines, not mandatory:

Stomach (to 5 cc): < 25 Gy
 Duodenum (to 5 cc): < 25 Gy
 Small bowel (to 5 cc): < 25 Gy
 Heart max (30cc): < 30 Gy
 Great vessel max (0.5 cc): < 60 Gy
 Skin (external) max (0.5 cc): < 32 Gy
 Chest wall max (0.5 cc): < 50 Gy
 Gallbladder max (0.5 cc): < 55 Gy
 Common bile duct max (0.5 cc) < 50 Gy (even though the bile duct is not often well visualized, it is always within the portal region and may be within high dose volumes for central targets, so efforts to reduce hot spots in this region are warranted)

5.6 Timing of Radiation

5.6.1 The first radiation treatment should begin within 7 days of the second TACE. Acceptable variation would be within 21 days of completion of TACE.

5.6.2 Per protocol, all external beam radiation treatments should be delivered within 15 calendar days. An acceptable variation is 16-21 calendar days. Treatment requiring greater than 22 calendar days constitutes a major protocol variation.

5.7 PTV coverage: The intent is for the prescription dose to cover 95% of the PTV. The PTV should be treated to as high a dose as possible, respecting normal tissue constraints, as a dose response has been observed. Modifying a PTV due to close proximity of adjacent OARs is not permitted. An acceptable variation per protocol would be 90-95% PTV coverage.

5.8 Radiation Therapy Adverse Events

The criteria used for the grading of toxicities encountered in this study are Common Toxicity Criteria (CTC) version 4.0.

Very likely (80-90%)

- Fatigue (which generally goes away after the radiation therapy is completed)
- Skin irritation, redness, itchiness, discomfort
- Temporary changes in blood work (decrease in blood counts, increase in liver enzymes), without symptoms

Less likely (30%)

- Nausea, vomiting (during therapy) – more common if stomach or gastrointestinal track irradiated
- Gastric, esophagus, small bowel or large bowel irritation/ulceration, bleeding, fistula, obstruction or changes in motility following therapy (may require medications or surgery) (<10% permanent changes)
- Chest wall pain, rib fracture (< 10%)

Less likely, but serious (<20%)

- Radiation-induced liver disease (RILD) (<5%). Classic RILD is a clinical diagnosis of anicteric ascites, hepatomegaly and elevation of alkaline phosphatase relative to other transaminases that may occur 2 weeks to 3 months following radiation to the liver.
- Non-classic RILD includes elevation of liver enzymes and/or any decline in liver function within 12 weeks from start of therapy (~20%). RILD can lead to liver failure that could lead to death. There is an increased risk of liver toxicity in patients with large tumors and in patients with pre-existing liver disease.
- Permanent thrombocytopenia (<1%); this may lead to bleeding
- Kidney injury (<1%); this may lead to changes on imaging and more rarely the need for medication.

5.9 Radiation Therapy Toxicity Assessment During Therapy

Patients will be assessed at least once during radiation therapy for toxicity. Radiation therapy will be continued as long as there is no grade 3 or 4 toxicity. Treatment delays or discontinuation of radiation will be at the discretion of the treating physician.

5.9.1 Radiation Modification Table

TOXICITY	MODIFICATION
Hematologic	
Grade 1 or 2	Continue radiation
Grade 3	Hold radiation until \leq Grade 2, then continue
Grade 4	Hold radiation 1 week until \leq Grade 2, then continue
Gastrointestinal	
Grade 1 or 2	Continue radiation
Grade \geq 3 diarrhea	Hold radiation until \leq Grade 2, then continue
Grade 1 or 2 nausea or vomiting	Initiate anti-emetics prior to radiation and as needed and continue radiation
Grade 3 nausea or vomiting	Hold radiation until \leq Grade 2, then continue with anti-emetics prior to radiation and as needed
Hepatic	
Grade 1 or 2 AST or ALT	Continue radiation
Grade 3 but less than 10x upper limit of normal AST or ALT	Continue radiation
Grade 3 and $>$ 10x ULN AST or ALT	Hold radiation until improves to \leq grade 2, then resume
Grade 4 AST and ALT	Hold radiation for one week and until improves to \leq grade 2, then resume
Child-Pugh score $>$ 7	Hold radiation until improves to Child-Pugh score \leq 7
Other Non-hematologic	
Grade 1 or 2	Continue radiation
Grade 3	Hold radiation until \leq Grade 2, then continue
Grade 4	Discontinue radiation

6.0 DATA COLLECTION

6.1 Before enrollment, patients will be interviewed and assessed for meeting inclusion and exclusion criteria. Patients will also be assessed for ability to complete the protocol and follow up. Follow up and data collection will proceed as outlined below and summarized in Appendix D.

6.1.1 Pretreatment data will include the following parameters:

1. Demographics: age, sex, etiology of liver disease
2. Past Medical History: comorbidities
3. Related symptomatology
4. Performance status according to ECOG
5. Liver and renal function tests: bilirubin, AST, ALT, albumin, alkaline phosphatase, GGTP, BUN, creatinine, Na, INR, and platelet count
6. Serum alpha fetoprotein (AFP)
7. Tumor MRI with Gd-EOB metrics: size, number of tumors, tumor location, tumor necrosis, mean ADC of whole tumor and viable component
8. Liver MRI metrics: degree of hepatobiliary phase enhancement, mean ADC
9. Chest CT

6.2 A regular on treatment visit (OTV) will be used to assess acute treatment related toxicity according to CTCAE v. 4. In the event that there is a treatment break, patients will be seen at least once a week.

6.3 Three to 6 weeks following completion of SBRT, the patient will be seen in routine follow up to assess and manage any post-treatment complications. At that time of the first visit, blood work will be obtained as follows:

Liver and renal function tests: bilirubin, AST, ALT, albumin, alkaline phosphatase, GGTP, BUN, creatinine, Na, INR, and platelet count
 Serum alpha fetoprotein (AFP)

6.4 Routine follow up will be scheduled every 3 to 4 months from the completion of radiation (2 to 3 months after the initial one month visit). For medical necessity, patients can be sooner. In addition to assessment of toxicity according to CTCAE, blood work will be obtained as follows:

Liver and renal function tests: bilirubin, AST, ALT, albumin, alkaline phosphatase, GGTP, BUN, creatinine, Na, INR, and platelet count
 Serum alpha fetoprotein (AFP)

6.5 Every 3 to 4 months post-radiation, the patient will have an MRI with Gd-EOB-DTPA to assess tumor response (as outlined below) up to one year.

6.6 Every 6 to 8 months, the patient will have a CT of the chest, abdomen, and pelvis to assess for systemic disease. If clinically warranted, imaging can be obtained sooner. PET/CT might be used if clinically warranted.

6.7 If a patient received his/her TACE treatments and did not receive SBRT, he/she will nevertheless be followed by the same follow up schedule as above except for the OTVs and one month post-radiation visit.

6.8 Patients will be followed after one year per standard medical care.

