1.3 Secondary Objectives

1.3.1 To determine the time to progression (TTP) of the treated lesion.

1.3.2 To determine the overall survival (OS) of patients as defined from completion of treatment until death.

1.3.3 To determine the progression free survival (PFS) of patients as defined from the completion of treatment until disease progression in the treated lesion, liver, or distant metastases.

1.3.4 To determine the tolerability and toxicity of combination TACE and SBRT in this population.

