4.0 DELIVERY OF TACE

4.1 Initial TACE will be delivered per standard protocol

4.2 After 3 to 8 weeks following the intial TACE, patients will return for labwork and consideration for a second TACE to the same site. TACE will not be repeated if the bilirubin is > 3 ng/mL.

4.3 Prior to preceding to radiation therapy, the patient will have labwork done including CBC and LFTs to assess return to within grade 2 elevations of baseline labwork prior to proceeding onto radiation.

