Appendix D: Protocol Timeline and Required Interventions/ Studies

Time point	Activities
Enrollment	
 • Screening for eligibility • Consultation with Radiation Oncology • Consultation with Interventional Oncology • Consultation with Medical Oncology • History and physical including ECOG performance status • Baseline renal and liver function tests • Baseline chemistry and CBC • Baseline AFP • Baseline MRI with Eovist of the liver • Baseline CT of the chest
Study initiation – time “0”	
 • TACE #1
3 to 8 weeks post TACE #1	
 • Renal and liver function tests • TACE #2 • Simulation for SBRT
1 to 3 weeks post TACE #2	
 • Renal and liver function tests • SBRT
3 to 6 weeks post SBRT	
 • Follow up history and physical • Renal and liver function tests • AFP
3 to 4 months post SBRT	
 • Follow up history and physical • Renal and liver function tests • AFP • MRI with Eovist of the liver
6 to 7 months post SBRT	
 • Follow up history and physical • Renal and liver function tests • AFP • MRI with Eovist of the liver • CT of the chest
9 to 10 months post SBRT	
 • Follow up history and physical • Renal and liver function tests • AFP • MRI with Eovist of the liver
12 to 13 months post SBRT	
 • Follow up appointment

	
• Renal and liver function tests• AFP• MRI with Eovist of the liver• CT of the chest
14 months and beyond post SBRT	
• Follow up per standard of care

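### After the pre-SBRT CBC, no haemoglobin or white-cell count is required through the 12 to 13 month visit, so anaemia, neutropenia and lymphopenia reach the toxicity record only if found incidentally

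*Combined protocol and SAP*

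**What the plan says.** Section 1.3.4 makes it a secondary objective "To determine the tolerability and toxicity of combination TACE and SBRT in this population". Section 5.8 places "Temporary changes in blood work (decrease in blood counts, increase in liver enzymes), without symptoms" under its very-likely heading (80-90%).

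A CBC is named at two points only. Appendix D lists "Baseline chemistry and CBC" at enrollment, and 4.3 says that before radiation "the patient will have labwork done including CBC and LFTs".

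After SBRT, 6.3 (first visit, 3 to 6 weeks) and 6.4 (every 3 to 4 months) each set out the blood tests. Section 6.4 introduces its list with "In addition to assessment of toxicity according to CTCAE, blood work will be obtained as follows". The list in both sections is "Liver and renal function tests: bilirubin, AST, ALT, albumin, alkaline phosphatase, GGTP, BUN, creatinine, Na, INR, and platelet count", followed by AFP. In Appendix D, the row "3 to 6 weeks post SBRT" and the four later rows up to 12 to 13 months carry renal and liver tests and AFP, with no CBC. Section 8.1 refers to blood work only in general terms. Section 8.2 plans descriptive statistics for post-treatment complications.

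During SBRT, the table in 5.9.1 holds radiation for grade 3 or 4 haematologic toxicity, for AST or ALT above 10 times the upper limit of normal, and for a Child-Pugh score above 7. Sections 5.9 and 6.2 require a toxicity assessment in that period but name no laboratory test.

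**The concern.** A fall in counts that causes no symptoms cannot be graded from history and examination. It needs a count. Section 6.4 pairs CTCAE assessment with a list that supplies platelets and leaves out red and white cells. A site that follows the list as written has no haemoglobin or white-cell value from which to grade anaemia, neutropenia or lymphopenia. The descriptive complications table could then show none of these events because nobody had to look, and a reader could not tell that from true absence. Because 5.8 calls the changes temporary, the gap matters most at the 3 to 6 week and 3 to 4 month visits and less later.

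A related but separate worry is that a hold rule based on laboratory grades can act only if a test is done while there are still fractions to hold.

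**Working it through.** The plan states no figure on this point, so the main check is to set the laboratory requirements side by side.

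| Time point | Source | Blood counts required |
|---|---|---|
| Enrollment | 6.1.1 and Appendix D | Platelets (6.1.1); CBC (Appendix D) |
| Before SBRT | 4.3 | CBC |
| During SBRT | 5.9, 6.2 | None named |
| 3 to 6 weeks after SBRT | 6.3, Appendix D | Platelets only |
| 3-4, 6-7, 9-10 and 12-13 months after SBRT | 6.4, Appendix D | Platelets only |

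**Post-SBRT visits.** There are 1 + 4 = 5. Visits requiring haemoglobin, white cells or a differential: 0. Visits requiring platelets: 5. All five already include a blood draw.

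**Does the list include a CBC by implication?** The same wording appears in 6.1.1, 6.3 and 6.4. At baseline Appendix D adds a CBC to it, and before SBRT 4.3 names a CBC apart from liver tests. After SBRT no passage adds one.

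**Who can benefit prospectively.** Target 40, with the 30th patient enrolled on 11/19/2019 (8.1): 40 - 30 = 10 later patients. If all attend, that is 10 x 2 = 20 visits at the two early time points and 10 x 5 = 50 over all five.

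**First 30 patients.** Assume TACE #1 at enrollment and the longest scheduled intervals. For the 30th patient: 11/19/2019 + 56 days (8 weeks to TACE #2) + 21 days (3 weeks to SBRT) + 15 days (SBRT course) = 02/19/2020. Adding 4 months gives 06/19/2020, which is before version 8 of 10/22/20. On these assumptions the 30 x 2 = 60 early visits of that group can be recovered only from existing reports. Some of the last 10 may also have passed their early visits by that date.

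**Secondary point: time from SBRT start to the first clearly scheduled count of any kind (platelets at 3 to 6 weeks, that is 21 to 42 days after SBRT).**
- 15-day course (5.6.2): 15 + 21 = 36 to 15 + 42 = 57 days.
- Shortest usual pattern under 5.1.2 (Monday, Wednesday, Friday, Monday, Wednesday; 9 days from first to last fraction): from 9 + 21 = 30 days.
- Longest acceptable course (21 days, 5.6.2): up to 21 + 42 = 63 days.

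In every case the course is over before that count.

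**The case against.** The strongest reply is that the laboratory lists are loosely drafted, so a missing CBC shows little about intent. The Appendix D row "1 to 3 weeks post TACE #2" names only renal and liver tests, although 4.3 requires a CBC before radiation. Likewise 6.1.1 lists only platelets at baseline, although Appendix D asks for a CBC. This stands: the Appendix D rows are not exhaustive, and one should not infer that the authors meant to exclude the test. But each of those omissions is made good in another place. The post-SBRT omission is not, and it rests on the explicit lists in 6.3 and 6.4, not on Appendix D alone.

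Second, the toxicity assessments in 6.2 and 6.4, and the review of complications in 6.3, would take in any cytopenia that came to light. This also stands. The gap is in the test that would find the event, not in the duty to record it once found.

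Third, the only blood-count toxicity that 5.8 lists among its serious risks is permanent thrombocytopenia (<1%), which the platelet count covers, and laboratories may report platelets within a full count. Both are fair. They make the point smaller and the remedy easier, but nothing requires the other values to be obtained or collected.

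Fourth, on the hold rows, Appendix D does place renal and liver tests in the same row as SBRT, and 5.9 leaves delays to the treating physician. Since 4.3 puts its check before radiation and Appendix D gives no timing relative to the fractions, an on-treatment hepatic test is neither clearly required nor clearly absent. For haematologic toxicity no on-treatment test is named at all.

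**Conclusion.** The point holds as a minor one. From the pre-SBRT CBC to the end of study follow-up, haemoglobin, white cells and a differential are required at 0 of 5 scheduled visits. Anaemia, neutropenia and lymphopenia therefore count toward objective 1.3.4 only when found incidentally. Thrombocytopenia is covered, and the primary response analysis does not depend on any of this. The reading of the schedule is certain on the text. The effect on the toxicity results is not known, because the documents give no rate for these events and do not say how often a laboratory reports them with the platelet count.

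A reader might infer more than this, and the documents do not support it:
- *That cytopenias would go unrecorded even if found.* Sections 6.2 to 6.4 would capture them.
- *That 80-90% of patients will have a missed cytopenia.* That heading covers an item combining unspecified blood counts with liver enzymes, and it names neither anaemia nor neutropenia.
- *That 36 to 57 days is the protocol's own interval to the first count after SBRT starts.* It holds only for a 15-day course.

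The missing on-treatment test for the 5.9.1 hold rows is a separate matter of safety conduct and is less certain, above all for the hepatic rows.

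**What to change.** In 6.3 and 6.4, replace the platelet count with a CBC with differential on the draws already scheduled, and show it in the five post-SBRT rows of Appendix D. If only part is adopted, take the 3 to 6 week and first 3 to 4 month visits.

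For patients already treated, abstract haemoglobin and white cells where the existing laboratory report gives them. In the 8.2 summary, use the number of patients with a value as the denominator for each cytopenia, and show earlier and later patients separately. Ascertainment will differ between the two groups, and stating the denominator discloses that difference but does not remove it.

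The cost is small: laboratory and data-entry work for at most 50 visits in later patients, any remaining late visits of earlier ones, and chart-review time. No extra venepuncture is needed for this part.

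Optionally, add one draw at the 6.2 on-treatment visit with a CBC and liver tests (AST, ALT, bilirubin, albumin, INR), so that the haematologic and hepatic rows of 5.9.1 can operate. This costs one extra blood draw per patient still to be treated.

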1.0 INTRODUCTION

1.1 Study Design

This is a non-randomized pilot study to assess the objective response rate and durability of response of combination Trans-Arterial Chemoembolization (TACE) with immediate stereotactic body radiation therapy (SBRT) in the treatment of unresectable hepatocellular carcinoma (HCC). Eligible patients will be selected based on having a lesion greater than 3 cm which would make them ineligible for other local therapies such as TACE and thermal ablation (TA). Eligible, consented, and registered patients will be treated with two sessions of standard TACE with ethiodol separated by a 4-week interval. After ensuring adequate return to baseline liver function, the patients will then be treated with SBRT to the targeted lesion to 30-40 Gy in 5 fractions. Tumor response will be assessed using mRECIST criteria as well diffusion weight imaging (DWI) via Magnetic Resonance Imaging (MRI) surveillance. In addition, tolerability and toxicity will be recorded via CTCAE v. 5.0. The essential hypothesis of this study is that combination TACE and SBRT for > 3 cm HCC will produce higher response rates and durable control compared to historical controls of TACE alone.

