8.2 Data Analysis

Descriptive statistics (median, min-max, range, and percentages) will be provided for the pretreatment data such as demographics and comorbidities, and post-treatment complications. To assess the 1-year response rate in patients, one-sample binomial test will be conducted. For the secondary objectives,

descriptive analysis will be applied to determine the median survival times and Kaplan-Meier survival curves will be plotted for the endpoints:

- Time to progression
- Progression-free survival
- Overall survival

All analysis will be performed using SAS version 9.3 (SAS Institute Inc., Cary, NC, USA).

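### No clinical CTCAE assessment is scheduled between TACE #1 and SBRT, so clinical toxicity of the TACE phase may be under-recorded, especially in patients who never reach SBRT

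*Combined protocol and SAP*

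**What the plan says.** The secondary objective in 1.3.4 is "To determine the tolerability and toxicity of combination TACE and SBRT in this population". Section 1.1 adds in general terms that "tolerability and toxicity will be recorded via CTCAE v. 5.0", without naming a visit, a start date or a population.

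CTCAE assessment is tied to visits in two places. Section 6.2 states: "A regular on treatment visit (OTV) will be used to assess acute treatment related toxicity according to CTCAE v. 4". That this is a radiation visit follows from 5.9 ("Patients will be assessed at least once during radiation therapy for toxicity") and from 6.7, which drops it for patients who do not get SBRT. Section 6.4 then sets follow-up every 3 to 4 months, counted from the end of radiation: "In addition to assessment of toxicity according to CTCAE, blood work will be obtained as follows".

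Before SBRT, 4.2 says that "patients will return for labwork and consideration for a second TACE to the same site", with a bilirubin limit for repeating TACE. Section 4.3 asks for blood counts and liver tests, judged against a grade 2 threshold relative to baseline, before radiation may start. Appendix D lists renal and liver function tests at both points and no clinical toxicity assessment.

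Patients who have TACE but no SBRT stay on the follow-up schedule, "except for the OTVs and one month post-radiation visit" (6.7). The analysis text in 8.2 promises descriptive statistics for "post-treatment complications". It defines neither a safety population nor a date from which toxicity counts.

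**The concern.** TACE is half of the regimen under study, and two sessions come before any radiation. If nobody is asked about adverse events in a structured way until radiation begins, then pain, fever, infection, bleeding or encephalopathy after TACE is graded only if someone chooses to record it or the patient recalls it later. An analyst cannot reliably restore such events afterwards.

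The loss would not fall evenly. Section 4.3 lets patients go on to SBRT only once their laboratory values have recovered sufficiently, so patients with lasting TACE toxicity are among those who do not reach SBRT. They are also the patients with the fewest toxicity contacts. What is at stake is whether the answer to 1.3.4 describes the combination or mainly its second half.

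**Working it through.** **The plan's own figures.** The documents give no expected toxicity rate, so there is no toxicity figure to reproduce. The one calculated design figure is the 82% power in 8.1. With n = 40, a null response rate of 0.52 and an equal-tailed exact test, the upper rejection region is 28 or more responses (tail 0.0160) and the lower is 14 or fewer (tail 0.0228). Power at 0.75 is 0.8209. The figure reproduces, and this point does not affect it.

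**Scheduled contacts side by side.**

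| Time | Source | Scheduled | CTCAE assessment named? |
|---|---|---|---|
| 3 to 8 weeks after TACE #1 | 4.2, Appendix D | Renal and liver tests; decision on TACE #2 | No |
| 1 to 3 weeks after TACE #2 | 4.3, Appendix D | Blood count, renal and liver tests; grade 2 laboratory threshold | No; laboratory gate only |
| During SBRT | 5.9, 6.2 | At least one toxicity visit | Yes |
| 3 to 6 weeks after SBRT | 6.3, Appendix D | History, examination, laboratory tests | Not by name; complications are assessed |
| Every 3 to 4 months after radiation | 6.4 | Laboratory tests | Yes |

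After enrolment, the first history and physical examination in Appendix D is the one 3 to 6 weeks after SBRT.

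**Length of the window.** Shortest: 3 + 1 = 4 weeks. Longest: 8 + 3 = 11 weeks. Section 5.6.1 aims for radiation within 7 days of the second TACE and accepts 21 days. On that text the lower end could fall below 4 weeks; the upper end is the same. The two passages should be reconciled.

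**Patients who do not reach SBRT.** They lose the on-treatment visit and the one-month visit. The 6.4 visits remain, but the date from which these are counted does not exist for them. If they are counted from TACE #2 (assumption), with 3 months as 13 weeks and 4 months as about 17, the first named CTCAE visit falls 3 + 13 = 16 to 8 + 17 = 25 weeks after TACE #1. Section 6.7 also speaks of TACE treatments in the plural, so a patient stopped after TACE #1 is not clearly covered.

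**Possible size, as an illustration only.** Let *a* be the rate of grade 3 or higher events in the TACE phase and *b* the rate in the SBRT phase, both assumed. If the two are independent and every patient reaches SBRT, the any-phase rate is 1 − (1 − *a*)(1 − *b*). Patients with a TACE-phase event only number 40 × *a* × (1 − *b*). With *b* = 10%:

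- *a* = 5%: 1 − 0.95 × 0.90 = 14.5%; 40 × 0.05 × 0.90 = 1.8 patients
- *a* = 10%: 1 − 0.90 × 0.90 = 19%; 40 × 0.10 × 0.90 = 3.6 patients
- *a* = 20%: 1 − 0.80 × 0.90 = 28%; 40 × 0.20 × 0.90 = 7.2 patients

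If no TACE-phase event were graded, the reported rate would be 10% in each case. That condition makes these figures upper bounds under the assumed rates, because laboratory events can be graded from the scheduled draws and some clinical events may be picked up later.

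**The case against.** A reader might infer that TACE-phase toxicity is left out of the result altogether, or that the toxicity table will describe only patients fit enough to start SBRT. The documents do not support that, for four reasons.

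- The main clause of 6.7 keeps TACE-only patients in follow-up, and the 6.4 visits in that follow-up include CTCAE assessment. Of the two visits they lose, the one-month visit does not name CTCAE grading for anyone.
- Section 1.1 promises CTCAE recording for the regimen as a whole, not for SBRT alone.
- Liver toxicity is checked in the TACE phase by 4.2, 4.3 and Appendix D, and blood counts by 4.3, which applies a grade threshold. A patient held back for abnormal liver tests is identified.
- The phrase "post-treatment complications" is ambiguous. In 8.2 it stands opposite pretreatment data, which are collected before any TACE, so it can mean anything after treatment begins. In 6.3 it describes the visit after SBRT.

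All four points stand, and they rule out any claim of a demonstrated downward bias. They do not close the gap. Section 1.1 names no visit, and the data collection section that should carry it out has none in the TACE phase. The laboratory checks are written as gates rather than toxicity records. A single draw can miss an abnormality that has come and gone, and it does not capture non-laboratory events. A follow-up visit about 16 to 25 weeks after TACE #1 (on the assumed anchor) is late for grading acute events.

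It is also fair to say that toxicity is a secondary, descriptive objective of a single-arm pilot, with no formal test resting on it.

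**Conclusion.** The concern holds as a risk of under-recording and should be fixed. The firm part comes directly from the protocol: no clinical CTCAE assessment is scheduled for 4 to 11 weeks of a regimen whose toxicity is an objective, and neither a toxicity start date nor a safety population is defined. The selective part also follows from the text, since patients who do not reach SBRT have fewer toxicity contacts and no date from which to count the rest.

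How many events would be lost cannot be derived from the documents. The illustration above (about 2 to 7 of 40 patients) rests wholly on assumed rates and on no TACE-phase event being graded. Sample size, power and the primary analysis are unaffected.

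**What to change.** - **6.2 and Appendix D:** record CTCAE-graded adverse events since TACE #1 at the two existing contacts, before TACE #2 and before SBRT. State that the laboratory results obtained there count as toxicity data.
- **6.7:** give patients without SBRT a follow-up anchor date, such as the last TACE, and make clear that patients stopped after one TACE are included.
- **8.2:** use all patients who start TACE #1 as the toxicity denominator. Tabulate worst grade by phase (TACE, SBRT, follow-up) and overall, with reasons for not reaching SBRT.
- **Grading version:** reconcile 1.1 (CTCAE 5.0), 5.8 (CTC 4.0) and 6.2 (CTCAE 4), so that one scale applies across phases.

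Going forward, the cost is a short case report form addition and one or two tables. The larger cost is retrospective. Section 8.1 dates the 30th enrolment to November 2019 and this protocol version is dated October 2020, so prospective recording can reach at most 40 − 30 = 10 patients. TACE-phase events for at least 30 of 40 would have to be abstracted from source records, and the report should say which patients were graded in which way. The reported toxicity rate will probably look less favourable.
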